9.2. Study participants retention

The study participant retention is critically important and every effort will be made to increase participants' adherence to their intervention and follow-up visit schedule. At weekly staff meetings, recruitment and retention will be discussed. Visits will be scheduled at the convenience of the patients. Personalized birthday, holiday, and anniversary cards will be sent to the participants. Small gifts will be used to improve participants' connection to the study and research staff.

10. Data collection

10.1. Measurements

- 1). Medical history: personal information (age, gender, marital status, occupation, education, household income, etc.), medical history including medications, and lifestyle risk factors (cigarette smoking, alcohol drinking, physical activity, and dietary habits).
 - 2). Anthropometric measurements: height, weight, waist circumference, hip

circumference.

- 3). Biochemical measurements: fasting plasma glucose, serum triglycerides, total cholesterol, LDL-C and HDL-C, liver enzymes, and uric acid.
 - 4). Insulin sensitivity: HOMA-IR.
- 5). Body composition will determine by IOI353 Body Composition Analyser (Jawon Medical, Gyeongsansi, South Korea).

10.2. Methods

A. Questionnaire

Demographic information: A self-report demographic questionnaire will be used to collect participant characteristics at baseline, including age, race/ethnicity, socioeconomic status (employment, education, and income), internet usage, and health status.

Medical history: Medical history including medication used will be self-reported by participants at the screening visit and subsequent follow-up visits. The medical recordings will be reviewed at times to ensure all the data are complete.

Diet: Three 24-hour dietary recalls will be conducted at baseline and during follow-up visits. Nutrient intake will be calculated using the China Food Composition table.

Physical activity: Physical activity will be recorded for 3 continuous days by Mi Band 2 Smart Bracelet (Xiaomi, Beijing, China).

B. Clinical examination

B1. Weight, waist circumference, and blood pressure

Height will be measured to the nearest 0.5 cm at baseline and follow-up visits using a wall-mounted stadiometer. Body weight will be measured to the nearest 0.1 kg in duplicate at each visit using a digital scale with participants dressed in light indoor clothes and without shoes. A gulick tape measure will be used to obtain duplicate measurements of waist and hip girths to the nearest 0.1 cm. Blood pressure will be measured in triplicate at each visit using the Omron HEM-907-XL automated sphygmomanometer. Participants will avoid exercise, smoking, coffee or tea for 30 minutes. Participants will be seated quietly for 5 minutes before measurement.

B2. Body composition

The bioelectrical impedance method will be used to measure body fat content using an IOI353 Body Composition Analyzer(Jawon Medical, Gyeongsansi, South

Korea) to evaluate the body fat, body muscle.

C. Biochemical tests

Overnight blood samples and spot urine will be collected to measure metabolic risk actors (plasma glucose, insulin, triglycerides, total cholesterol, LDL- and HDL-cholesterol, liver enzymes, and uric acid) using standard methods at the clincial laboratory of each subcenter.

11. Baseline and Follow-up Visits

11.1. Screening visit (V0)

A. Questionnaire

Demographic information: age, gender, education.

Medical history: personal history of acute or chronic viral hepatitis, drug-induced liver diseases, autoimmune hepatitis, Cerebral infarction, cancer, myocardial infarction, hyperthyroidism, hypothyroidism, and diabetes, or having a medical condition or taking medication that would limit metabolism or weight loss.

Medications: lipid-lowering, anti-hypertension, and liver-protection medication (specific drugs dosage and termination time).

Lifestyle risk factors: alcohol drinking and cigarette smoking.

B. Physical examination

Height, weight, waist circumference, hip circumference, and blood pressure;

C. Laboratory examination

Regular blood and urine tests

Liver enzymes

Serum triglycerides, total, LDL-C and HDL-C, and plasma glucose, insulin, uric acid

D. Other examinations

Electrocardiograph (ECG)

Body composition analyzation for body fat

11.2. Randomization visit (V1)

A. Questionnaires

Assessment of three 24-hour dietary recalls

Assessment of baseline physical activity (for 3 continuous days)

B. Measurements of the primary and secondary outcomes

anthropometric examination.

Measurement of body fat distribution by Body composition analyzer(Jawon Medical, Gyeongsansi, South Korea)

C. Collection of blood

D Randomization:

Participants will be allocated into the NC group, LC diet group, CR diet group and LC+CR diet group using a computer program.

11.3. Week 0 visit (V2)

A. Exercise and dietary records will be reviewed.

B. Dietary evaluation and adjustment:

Participants will be asked to be as specific as possible about the type and amount(g/ml) of food and beverage consumed (e.g. skimmed or non-skimmed milk, 200ml), including type of cooking method used (e.g. roasted, boiled, etc.) by a 24-hour dietary recalls (3 days including two working days and one weekend day). Dietitians estimate and record the total intakes of calories(kcal), protein (%), fat (%), carbohydrates (%) according to the China Food Composition table.

C. Height, body weight, waist circumference, hip circumference, will be recorded at the end of every month.

11.4. Week 4 visit (V3)

A. Questionnaires

Assessment of three 24-hour dietary recalls

Assessment of baseline physical activity (for 3 continuous days)

B. Physical examination: height, weight, waist circumference, hip circumference, body fat

C. Laboratory examination:

Routine tests for blood, serum lipids, liver enzymes, uric acid, fasting plasma glucose, serum insulin

D. Evaluation and adjustment of dietary.

11.5. Week 8 visit (V4)

A. Questionnaires

Assessment of three 24-hour dietary recalls

Assessment of baseline physical activity (for 3 continuous days)

B. Physical examination: height, weight, waist circumference, hip circumference, body fat

C. Laboratory examination:

Routine tests for blood, serum lipids, liver enzymes, uric acid, fasting plasma glucose, serum insulin

D. Evaluation and adjustment of dietary.

11.6. Week 12 visit (V5)

A. Questionnaires

Assessment of three 24-hour dietary recalls

Assessment of baseline physical activity (for 3 continuous days)

B. Physical examination: height, weight, waist circumference, hip circumference, body fat

C. Laboratory examination:

Routine tests for blood, serum lipids, liver enzymes, uric acid, fasting plasma glucose, serum insulin

D. Evaluation and adjustment of dietary.

11.7. Monitoring and quality control

- A. Dietitians and nurses will receive training on data collection or intervention procedures.
- B. Exercise and dietary will be supervised by study staff.
- C. Compliance to exercise will be recorded by a Mi Band 2 Smart Bracelet (Xiaomi, Beijing, China) and accessed by study staff weekly.
- D. Plasma glucose, lipid, and liver enzymes will be determined at the each subcenter with stringent quality control.
- E. All study outcomes will be measured by trained staff using a stringent quality control process. Participants will be informed not to eat, smoke, drink, or do any strenuous exercise at least 10 hours before the examination at each visit.

12. Safety and Adverse Events

12.1. Safety measures and laboratory examinations

All participants will be evaluated for their pulse rate and blood pressure before intervention and will be evaluated for any physical discomfort, including eart palpitations, chest pain, constipation, gastrointestinal discomfort and hypoglycaemia

during intervention. The occurrence, severity, and duration of physical discomfort will be recorded.

12.2. Definition of adverse events

All medical adverse events will be recorded and the causal relationship to the exercise intervention will be further evaluated. The relevant adverse events are defined as heart palpitations, chest pain, constipation, gastrointestinal discomfort and hypoglycaemia during intervention.

12.3. Recording of adverse events

Any medical adverse events, including physical discomfort or abnormal laboratory examinations, will be recorded. Additionally, the nature, severity, and causal-effect relationship will be evaluated by physicians and recorded in a timely manner on case report forms.

12.4. Definition of a causal-effect relationship

With regard to the causal-effect relationship, medical adverse events are divided into five categories: definite, probable, possible, unlikely, and unrelated. Only "definite" and "probable" are counted as adverse events.

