6.2. Masking

This is an open-label trial.

7. Intervention

This trial aims to test the effects of different diets on weight loss and metabolic risk factors. The duration of the intervention is 12 weeks.

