7.1. Intervention programs

NC group

Participants in the NC group were designed to follow a non-restricted-calorie

diet with 55-65% of calories from carbohydrate, 30% from fat and 20% from protein[19, 31–32]. Participants will not be food choice restricted but they should avoid overeating. No specific exercise program will be recommended.

LC group

Participants assigned to the LC diet group were instructed to follow a non-restricted-calorie diet with less than 26% of calories from carbohydrates, 50% from fat and more than 24% from proteinc[15, 29-30]. Participants will receive free standard LC replacement, a nutritional bar (Nanda Fit Nutrition and Health Consulting Co., Ltd, Guangzhou, China) both at lunch and dinner (370kcal totally, specific formula shown in **Table 1**). Participants will not be food choice restricted but they should avoid overeating. Participants will be instructed to drink 2L water/day and to minimize fruits, bread, added sugars, refined white flour products, and sources of trans fats. No specific exercise program will be recommended.

CR group

Participants in the CR diet group were restricted daily calorie to 1,200-1,500kcal with 55-65% of calories from carbohydrate, 30% from fat and 20% from protein[29-30,32]. Participants will not be food choice restricted. No specific exercise program will be recommended.

LC+CR group

Participants assigned to LC+CR diet group were instructed to follow a daily calorie intake of 1,200-1,500kcal with less than 26% of calories from carbohydrate, 50% from fat and more than 24% from protein[29-31]. Participants will receive free standard LC replacement, a nutritional bar (Nanda Fit Nutrition and Health Consulting Co., Ltd, Guangzhou, China) at lunch and dinner (370kcal totally, specific formula shown in **Table 1**). Participants will not be food choice restricted and will be instructed to drink 2L water/day and to minimize fruits, bread, added sugars, refined white flour products, and sources of trans fats. No specific exercise program will be recommended.

Table 1. The Components of the Nutrition Food Bar

Content	Per 100 grams	NRV%
Energy	1723KJ	20
Protein	32.2g	54
Fat	15.7g	26

Trans Fatty Acids	0g	/
Carbohydrate	29.2	10
Meal Fiber	12.7g	51
Sodium	65mg	3

Master formula: whey protein, soy protein isolate, chia seed, oligosaccharide, Collagen, konjac extract, γ-aminobutyric acid.

NRV, nutrient reference values

Health education

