All the participants will meet in weekly counseling sessions by dietitians to provide dietitian plans and give advice for 12 weeks. Guidance on counting macronutrients, reading nutrition labels and detailed dietary recipes will be given to four groups. All study participants were instructed to record macronutrients, nutrition labels and detailed dietary recipes all they consume whole day for 3 days per week, including 2 working days and 1 weekend day. Nutrient intake will be calculated based on the nutrient content listed in the Chinese Food Composition Table[33]. Furthermore, trial participants will be required to wear a Mi Band 2 Smart Bracelet (Xiaomi, Beijing, China) during the whole experimental process to record their regular physical activity. They were advised to do regular exercise 3 times a week with durations for 30 minutes. During each follow-up visit, participants will be asked about adverse reactions such as hunger, fatigue, palpitation, anorexia, constipation, alopecia. Research assistants will meet participants weekly to assess their compliance and provide advice on adherence to the diet program.

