13.3. Dropout management

Physicians should complete the case report form and record the reason for dropping out. Physicians should also assess the causal-effect relationship of the intervention with adverse events and collect detailed data related to the last exercise session. The data from subjects who have dropped out will be stored and used for intention-to-treat analysis

14. Ethical requirements

The study followed the ethical guidelines of the Helsinki Declaration and obtained the approval of the Ethics Committee of Zhujiang Hospital of Southern Medical University (ratification No.:2018-NFMDXK-001), the host research unit, and complete registration at the China Clinical trial Registration Center (registration number: ChiCTR1800015156).

15. Data management

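### Section 12.4 counts an event as adverse only if it is graded definite or probable, and 12.2 grades causality against an exercise intervention that is not randomised, so the reported tally would be too low and could differ by arm.

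*Protocol*

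**What the plan says.** - **Recording.** Section 12.3: "Any medical adverse events, including physical discomfort or abnormal laboratory examinations, will be recorded". Section 12.2 likewise has all medical adverse events recorded. Under 12.3, physicians evaluate nature, severity and causality and enter them on the case report form.
- **Counting.** Section 12.4: "medical adverse events are divided into five categories: definite, probable, possible, unlikely, and unrelated". The next sentence is the counting rule: "Only 'definite' and 'probable' are counted as adverse events".
- **Exposure for causality.** Section 12.2: "the causal relationship to the exercise intervention will be further evaluated". For drop-outs, section 13.3 tells physicians to "collect detailed data related to the last exercise session", although the same sentence also asks for the relationship of events to the intervention in general terms.
- **What is tested.** The opening of section 7: "This trial aims to test the effects of different diets on weight loss and metabolic risk factors". For each of the four groups, section 7.1 says: "No specific exercise program will be recommended".
- **Events solicited.** Section 7.1, under health education, says that at each follow-up visit "participants will be asked about adverse reactions such as hunger, fatigue, palpitation, anorexia, constipation, alopecia". The relevant events named in 12.2 are palpitations, chest pain, constipation, gastrointestinal discomfort and hypoglycaemia.
- **Severe events.** Section 12.6 defines them by outcome, including death and hospitalisation, and requires a report within 24 hours. It states no causality condition.
- **Masking.** Section 6.2 makes the trial open-label.

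**The concern.** An adverse event is normally defined without regard to cause, and relatedness is a separate attribute. Section 12.4 makes relatedness part of the definition. Events that physicians considered possibly due to the diet are then discarded along with those considered unrelated.

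Two features make this worse. First, the exposure named for the causality judgement in 12.2 is exercise, which no arm is randomised to. A grader who follows that wording is asked the wrong question about constipation or hypoglycaemia on an assigned diet. Second, graders may know the arm. An event in a participant on a restricted diet with a nutrition bar may be attributed more readily than the same event in the control group. The filter can therefore distort the comparison between arms as well as lower the level.

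At stake is the comparative safety summary of four diets. Section 15.3 also lists adverse events among the standard reports used for study management, so the same filtered count could be what management sees during the trial.

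**Working it through.** The protocol states no adverse-event rate or safety power, so there is no figure to reproduce. The check is a comparison of sections, followed by an illustration on assumed rates.

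**1. Recorded versus counted.** Sections 12.2 and 12.3 record everything. Section 12.4 counts 2 of 5 causality grades; possible, unlikely and unrelated are left out. The counted total can never exceed the recorded total, and is lower as soon as one event receives any of the other three grades.

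**2. Named exposure versus randomised exposure.** Sections 3.1 and 7 randomise diets. Section 7.1 says of every arm that no specific exercise programme is recommended. Under health education it nevertheless advises all participants to exercise three times a week for 30 minutes; section 7.2 tells them not to change their physical activity; and section 11.7 records exercise compliance. These passages conflict and must be reconciled, but on any reading exercise is common to all arms and is not the intervention under test. The wording in 12.2 and the exercise clause in 13.3 therefore point at the wrong exposure.

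**3. Who grades.** Physicians do (12.3), in an open-label trial (6.2). No masking of the causality grading is stated. The blinding in section 17 concerns technologists, and that in 15.3 keeps reports from staff who collect outcomes.

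**4. Event lists.** Section 12.2 names 5 events and section 7.1 names 6. Two are shared (palpitation, constipation). Only in 7.1: hunger, fatigue, anorexia, alopecia. Only in 12.2: chest pain, gastrointestinal discomfort, hypoglycaemia. The union has 5 + 6 − 2 = 9 events.

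**5. Illustration.** Let p be the share of participants in an arm with an event and s the share of those events graded definite or probable. The counted rate is p × s, and the expected count is 75 × p × s, with 75 per arm from section 3.2. Both p and s are assumptions.

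*Different attribution by arm.* Take p = 20% in both arms, s = 50% in a low-carbohydrate arm and 20% in control:
- counted rates: 0.20 × 0.50 = 10% and 0.20 × 0.20 = 4%;
- expected counts: 7.5 and 3;
- apparent ratio: 10/4 = 2.5, with no true difference. When p is equal, the ratio is simply s₁/s₂.

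*Same attribution in both arms.* With p̄ the mean of the two counted rates p₁ and p₂, the power of a two-sided 0.05 comparison is Φ((d − 1.96·se₀)/se₁), where d = |p₁ − p₂|, se₀ = √(2p̄(1 − p̄)/75) and se₁ = √((p₁(1 − p₁) + p₂(1 − p₂))/75).

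| s | Counts, true 30% v 10% | Difference | Power | Counts, true 20% v 10% | Difference | Power |
|---|---|---|---|---|---|---|
| 100% | 22.5 v 7.5 | 20 points | 87% | 15 v 7.5 | 10 points | 40% |
| 75% | 16.9 v 5.6 | 15 points | 73% | 11.3 v 5.6 | 7.5 points | 31% |
| 50% | 11.3 v 3.8 | 10 points | 53% | 7.5 v 3.8 | 5 points | 21% |
| 25% | 5.6 v 1.9 | 5 points | 29% | 3.8 v 1.9 | 2.5 points | 12% |

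Even an even-handed filter shrinks a true difference in proportion to s.

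**The case against.** The best defence is that nothing is lost at source. Every event goes on the case report form with its grade, so an all-cause table by arm can still be made, and the statistical analysis plan, which is not at hand, may provide one. Adverse events are neither a primary nor a secondary outcome, and section 16 plans no specific test of them. No efficacy inference, power or alpha depends on 12.4. All of this stands, and it limits the point to the reported tally. It does not remove the point: the counting rule is in the protocol itself, and a safety table that follows it would be filtered.

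A reader might infer four stronger things that the document does not support.

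- *A hospitalisation graded possible would be lost.* Section 12.6 defines severe events by outcome and requires a report without reference to cause. What is shown is that 12.4 and 12.6 do not fit together, not that such an event would go unreported.
- *Hardly any diet harm could ever count.* This rests on one phrase in 12.2. Section 12.4 names no exposure, and 13.3 also speaks of the intervention generally, so a physician could reasonably grade against the diet. The exercise wording is wrong, but it does not prove that diet harms cannot be counted.
- *Hunger, fatigue, anorexia and alopecia are asked about weekly and then excluded.* Section 7.1 ties the question to each follow-up visit, and the visits scheduled after week 0 in section 11 are weeks 4, 8 and 12. The weekly contacts are described for counselling and compliance. Nothing says that an event missing from the 12.2 list goes unrecorded.
- *A particular size of bias.* The 2.5-fold ratio and the power losses follow from assumed rates and say nothing about what this trial will see.

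**Conclusion.** The point holds for the reported tally. As written, section 12.4 defines adverse events by attribution, against the all-event recording in 12.2 and 12.3, and section 12.2 names an exposure that the trial does not randomise. A tally that follows 12.4 is too low whenever any event is graded possible, unlikely or unrelated; that direction needs no assumption. A difference between arms is a risk rather than a certainty. It arises if physicians who know the diet attribute events unevenly, and the protocol states no safeguard against this.

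The size cannot be fixed from the document. It depends on the share of events graded definite or probable, which is not given; over assumed shares of 25% to 75%, the counted difference is 25% to 75% of the true one. The loss is recoverable because the underlying records are kept.

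**What to change.** 1. Delete the counting sentence in 12.4. Define an adverse event without regard to cause and report all events by randomised arm, with relatedness shown separately.
2. In 12.2 and 13.3, replace the exercise references so that relatedness is judged against the assigned diet and, in the arms that receive it, the nutrition bar.
3. Reconcile 12.4 with 12.6, so that it is explicit that severe events are both reported and counted whatever their causality grade.
4. Make the 12.2 list the union of its present events and those asked about in 7.1: add hunger, fatigue, anorexia and alopecia, and remove none. Simply matching 12.2 to the 7.1 list would drop chest pain, gastrointestinal discomfort and hypoglycaemia.
5. Reconcile the conflicting exercise statements in 7.1, 7.2 and 11.7, so that the safety section has a consistent text to refer to.

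The cost is wording and longer safety tables. The plan already requires all events to be recorded, so step 1 needs no new data collection.

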12.5. Assessment of severity

The severity of adverse events is categorized at three levels as follows:

Mild: usually temporary and not affecting daily activities.

Moderate: causing discomfort and affecting daily activities, though tolerable and not requiring participants to take any medication.

Severe: disrupting daily activities and intolerable, requiring participants to take medication immediately.

Treatment Physicians will observe and record the progress of adverse events and keep track of those participants who have dropped out until the adverse events have completely subsided. Additionally, physicians will evaluate those adverse events for a causal-effect relationship.

12.6. Severe adverse events

Definition:

According to the definition by the Food and Drug Administration, USA, severe adverse events are defined as any of the following:

Life-threatening experience

Death:

Inpatient hospitalization or prolongation of existing hospitalization

A persistent or significant disability/incapacity

A congenital anomaly/birth defect

Reporting of severe adverse events

If severe adverse events occur in participants, physicians should immediately provide the appropriate care to ensure their safety. Additionally, physicians will report the adverse events and treatment to the Principal Investigator and the Committee within 24 hours and complete the report form.

